#### **4.1. Study Samples (Analysis Sets)**

We plan to include all readers' interpretations of all cases in the analysis set. If any protocol deviations or violations occur the statistician will evaluate these to determine their impact on the

validity of the study data; and will determine whether any affected data points should be excluded from analysis.

Unit of analysis. The unit of analysis on this study is the subject (case).

#### **4.2. Treatment Assignment**

This is a retrospective study for which imaging and clinical management occurred prior to case selection. All cases will be evaluated the same way by all study readers, such that there are no treatment assignments or treatment groups.

#### **4.3. Multiple Centers (Pooling)**

Fujifilm obtained images from multiple centers. The protocol for data submission, quality review passed by all images, and reference standard status determination for all images used in the pilot MRMC study were common. Cases will be pooled across enrolling centers for interpretation on the pilot MRMC study using common interpretation protocol and eCRFs, and results of interpretation sessions will be monitored. The scoring of (lesion matching for) reader interpretations will follow a common process. Results for any particular reader therefore will be pooled across enrolling centers.

#### **4.4. Derived Variables**

Per-subject BI-RADS, POM, and recall scores requiring correct lesion localization will be derived as shown below. The general principle is that even at the subject level, credit is only given for identifying a subject with cancer if the reader marks findings in at least one location with cancer. Findings that do not match the location of a malignant lesion are ignored for cancer cases in the per-subject analyses but may be reported, generally in an appendix.

When computing sensitivity and specificity based on BI-RADS, a score of 4 or 5 constitutes a positive test result. A cutoff score of BI-RADS 3 or higher may also be used to compute the sensitivity and specificity in secondary analyses.

Per-Subject Scoring: POM and BI-RADS. The primary endpoint is per-subject AUC based on POM scores requiring correct lesion localization. Secondary endpoints include per-subject sensitivity requiring correct lesion localization and specificity based on BI-RADS categories. Scores for use in these analyses will be derived by the statistician as summarized in **Table 1** on page 13.

Per-Subject Scoring: Recall. Secondary endpoints include per-subject recall rate for non-cancer cases and separately for cancer cases requiring correct lesion localization, based on a separate yes/no question. Scores for use in this per-subject analysis will be derived by the statistician as summarized in **Table 2**.

True Positive, False Negative, True Negative, and False Positive. In per-subject analysis of sensitivity and specificity:

- A true positive (TP) occurs when a case contains one or more cancerous lesions and the per-subject BI-RADS score requiring correct lesion localization is 4 or 5.
- A false negative (FN) occurs when a case contains one or more cancerous lesions and the per-subject BI-RADS score requiring correct lesion localization is 1, 2, or 3.
- A true negative (TN) occurs when a case does not have any cancerous lesions and the per-subject BI-RADS score is 1, 2, or 3.
- A false positive (FP) occurs when a case does not have any cancerous lesions and the per-subject BI-RADS score is 4 or 5.

When computing recall rates requiring correct lesion localization, a recall occurs when a case has per-subject recall score equal to yes.

#### **4.5. Subgroups**

Analyses of per-subject recall rate for non-cancer cases and specificity are limited to the subgroup of cases without cancer. Analyses of per-subject sensitivity and per-subject recall rate for cancer cases are limited to the subgroup of subjects with cancer. We may also 1) analyze AUC, sensitivity, specificity, and/or recall rate in the subgroup of women with dense breasts; and/or 2) perform per-lesion analysis of sensitivity in subgroups defined by lesion type (masses with or without calcifications, focal asymmetries, and/or architectural distortions in one subgroup, and calcifications in another subgroup).

**Table 1. Per-Subject POM and BI-RADS Scores Requiring Correct Lesion Localization**

Reference standard	Reader's interpretation	Per-Subject POM and BI-RADS
No malignancies in this case	No findings in this case	
POM: Same as POM recorded by the reader for the case.
 
BI-RADS: Same as category recorded by the reader for the case.
 
From Initial Mammographic Findings form page.

	One or more findings in this case	
POM: Overall POM recorded by the reader for the case.
 
BI-RADS: Overall category recorded by the reader for the case.
 
From Overall Patient Recall form page.

One or more malignancies in this case 	No findings in this case	
POM: Same as POM recorded by the reader for the case.
 
BI-RADS: Same as category recorded by the reader for the case.
 
From Initial Mammographic Findings form page.

	Findings in this case, but no findings matching the location(s) of any proven malignancies in this case	
POM: Assigned as the higher of 0 or, for readers who do not assign POM 0 to any case in a reading modality, the minimum POM score assigned by that reader in that modality.
 
BI-RADS: Assigned as category one (1).

	One or more findings correctly matching the location(s) of any proven malignancies in this case	
POM: Highest POM score recorded by the reader for any of these matched findings.
 
BI-RADS: Highest category recorded by the reader for any of these matched findings.

If the case contains more than one malignant lesion, the reader will get credit for identifying the case as having one or more proven malignancies even if the reader does not identify all of the proven malignancies in the case. For example in a bilateral case, the reader would get credit for identifying the case even if the reader marks findings in only one breast.

The POM scores and BI-RADS categories for any reader findings in this case that do not match the location(s) of any proven malignancies will be ignored in the per-subject analysis, which requires a single POM score and single BI-RADS category per subject conditional on whether the subject does or does not have proven malignancies.

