**Table 5. Per-subject POM and BI-RADS scores (requiring correct lesion localization)**

Reference standard	Reader's interpretation	Per-subject POM and BI-RADS
No malignancies in this case	No findings located in this case	POM: Same as POM recorded by the reader for the case BI-RADS: Same as category recorded by the reader for the case
	One or more findings located in this case	POM: Overall POM recorded by the reader for the case BI-RADS: Overall category recorded by the reader for any of those findings
One or more malignancies in this case	No findings located in this case	POM: Same as POM recorded by the reader for the case BI-RADS: Same as category recorded by the reader for the case
	Findings in this case, but no findings matching the location(s) of any proven malignancies in this case	POM: Assigned as the higher of zero (0) or, for readers who do not assign POM 0 to any case in a reading modality, the minimum POM score assigned by that reader in that modality. BI-RADS: Assigned as category one (1)
	One or more findings correctly matching the location(s) of any proven malignancies in this case	POM: Highest POM score recorded by the reader for any of those findings BI-RADS: Highest category recorded by the reader for any of those findings

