### 11.3.3 True Positive, False Negative, True Negative, and False Positive

#### In per-subject analysis:

- A true positive (TP) occurs when a case contains one or more cancerous lesions, and the per-subject BI-RADS score is 4, or 5. This happens when the reader marks one or more findings, at least one of those findings matches the location of one or more cancerous lesions, and the reader assigns a BI-RADS category 4 or 5 to at least one such finding.
- A false negative (FN) occurs when a case contains one or more cancerous lesions, and the per-subject BI-RADS score is 1, 2, or 3. This happens when either: 1) the reader does not mark any findings that match the location of one or more cancerous lesions, or 2) the reader marks one or more findings, at least one of those findings matches the location of one or more cancerous lesions, but none of the scores assigned to those findings are higher than BI-RADS 3.

- A true negative (TN) occurs when a case does not have any cancerous lesions, and the per-subject BI-RADS score is 1, 2, or 3. This happens when either: 1) the reader does not mark any findings in the case, or 2) the reader marks one or more findings in the case, but none are higher than BI-RADS 3.
- A false positive (FP) occurs when a case does not have any cancerous lesions, and the per-subject BI-RADS score is 4, or 5. This happens when the reader marks findings in a case containing no cancerous lesions, and assigns a BI-RADS category 4 or 5 to at least one such finding.

When computing recall rates requiring correct lesion localization, a recall occurs when a case has per-subject recall score equal to yes. This happens whenever the reader recalls a non-cancer case; or when the reader recalls a cancer case and marks one or more findings and at least one of those findings matches the location of one or more cancerous lesions.

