### **3.4. Image Interpretation Results**

Readers will be prompted by scribes, who will enter each reader’s responses in the reader eCRF (**Appendix 1**). For each case on each read, the reader will first note whether there are mammographic findings. If the answer to this question is “no” the reader will be asked to provide a BI-RADS assessment category of 1 or 2, a probability of malignancy (POM) score in 0% through 100%, and a recall decision of “no.” If the reader answers “yes” to whether there are mammographic findings the reader will be asked to confirm an initial BI-RADS assessment category of 0, and will then provide detailed information for up to three (3) suspicious findings (reader lesions):

- Location (including breast [right or left], diagram location [1 – 9 or combinations when the finding is in multiple diagram sections] within view [right CC, left CC, right MLO, left MLO], and coordinates for each of CC and MLO [N/A if not seen on that view; or X, Y, and for DBT only, Slice])
- Type, as mass, asymmetry, calcification, architectural distortion, or other with description. The reader may check all that apply.
- Forced BI-RADS assessment category 1, 2, 3, 4, or 5
- POM in 0% through 100%

The reader will then be asked for her or his overall recall decision (yes or no), forced BI-RADS assessment category, and POM score, for the case.

In cases with mammographic findings, consistency of BI-RADS scores, POM scores, and recall decisions will not be forced – for example, readers will be permitted to use the full range of POM scores for a finding no matter what BI-RADS score they assign to it.

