### OVERALL PATIENT RECALL

31. Overall, would you recall this subject?  Yes  No

32. Overall, what is your forced BI-RADS score for this subject? (check one)

 1	 2	 3	 4	 5
----------------------------	----------------------------	----------------------------	----------------------------	----------------------------

33. Overall, what is your estimated probability of malignancy for this subject (0-100%)? 

--	--	--

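### Does it matter that non-cancer cases with findings are scored from the reader's overall rating while matched cancers are scored from lesion ratings?

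*SAP*

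**What the plan says.** The reader form collects two layers of rating when findings are marked. Each of up to three lesions gets a forced BI-RADS category and a POM. SAP 3.4 then adds a case-level layer: "The reader will then be asked for her or his overall recall decision (yes or no), forced BI-RADS assessment category, and POM score". On the Overall Patient Recall page of the form this appears as, for example, "Overall, what is your forced BI-RADS score for this subject".

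SAP Table 1 uses the layers differently by truth status:

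- **Non-cancer, findings marked:** BI-RADS is "Overall category recorded by the reader for the case". POM is also the overall value, and the table names the Overall Patient Recall page as the source of both.
- **Cancer, at least one finding matched:** BI-RADS is "Highest category recorded by the reader for any of these matched findings", and POM follows the same rule.

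Footnote 2 to the table states that the single score per subject is "conditional on whether the subject does or does not have proven malignancies".

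Protocol Table 5 gives the same POM rule for non-cancers with findings: "Overall POM recorded by the reader for the case". Its BI-RADS cell reads "Overall category recorded by the reader for any of those findings", which mixes the case level and the lesion level. Protocol 11.3.3 defines a false positive by a per-subject score of 4 or 5, then adds an explanation at finding level: "the reader marks findings in a case containing no cancerous lesions, and assigns a BI-RADS category 4 or 5 to at least one such finding". SAP 4.4 keeps the per-subject definition and omits that explanation. SAP section 1 says the SAP prevails if the two documents conflict.

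**The concern.** An ROC analysis compares scores between cancers and non-cancers, so a reader would expect both groups to be scored on the same scale from the same question. Here a matched cancer is scored by a lesion rating and a marked non-cancer by a separate summary rating given afterwards. Nothing in the documents requires the summary to equal the highest lesion rating. If readers tend to soften or raise it, absolute AUC and specificity move for reasons unrelated to the images.

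The protocol seems to add a second problem. A non-cancer whose worst lesion is rated 4 but whose overall category is 3 is a true negative under SAP Table 1 and a false positive under the explanatory sentence in Protocol 11.3.3. SAP section 5 lists no cross-tabulation of the two ratings, and no sensitivity analysis addresses the choice.

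At stake are the average AUC within each modality, which SAP 4.10 names as an input to sizing the pivotal study, and specificity, which SAP 4.6.2 explores to plan the pivotal secondary endpoints.

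**Working it through.** **Is there one executable rule?**

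- *POM (primary endpoint).* SAP Table 1 and Protocol Table 5 both use the overall POM for a non-cancer with findings. There is no conflict.
- *BI-RADS (specificity).* SAP Table 1 names the overall category and the form page. SAP 4.4 defines true negative and false positive by the per-subject score alone. The defining clauses of Protocol 11.3.3 also use the per-subject score; only the explanations that follow are at finding level. The precedence clause settles what remains. The case rated lesion 4, overall 3 is a true negative, and the programmer has no choice to make.

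**Why the sources differ.** In a cancer the overall rating may be driven by a mark away from the malignancy, so a localization-based score has to come from matched lesions. A non-cancer has no malignant lesion to match, and the reader's own case rating is a natural per-subject score.

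**How large could the effect be?** The plan states no figure that depends on this rule, so there is none to reproduce. Inputs from the documents: 18 cancers, 82 non-cancers (17 + 19 + 46) and six readers.

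- One read crossing the BI-RADS cutoff of 4: 1/82 = 0.012 in that reader's specificity in one modality; 1/(6 × 82) = 1/492 = 0.002 in the six-reader average.
- One non-cancer takes part in 18 of the 18 × 82 = 1,476 pairs, so it can move a reader's AUC by at most 18/1,476 = 0.012.
- Five net discordant reads by one reader: 5/82 = 0.061 for that reader; 5/492 = 0.010 in the average.

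The AUC effect also needs POM distributions, which the documents do not give. The following are assumptions:

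- Cancers: 80% matched, POM normal with mean 60 and SD 20, clipped to 1–100; 10% unmatched at 0; 10% with no findings, POM 0–10.
- Non-cancers: 40% marked, highest lesion POM normal with mean 35 and SD 20, clipped to 1–100; the rest POM 0–10.

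With 400,000 draws per group, the AUC using lesion ratings throughout is about 0.77. The Hanley–McNeil standard error for 18 and 82 cases is about 0.068.

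| Overall minus highest lesion POM | Marked non-cancers affected | Change in AUC | Change in variance |
|---|---|---|---|
| -10 | 10% | +0.003 | about -1% |
| +10 | 10% | -0.004 | about +1% |
| -5 | all | +0.017 | about -5% |
| +5 | all | -0.018 | about +5% |
| -10 | all | +0.032 | about -9% |
| +10 | all | -0.038 | about +9% |

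If the share marked runs from 30% to 50%, the 10% rows become +0.002 to +0.004 and -0.003 to -0.005.

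**Between-modality difference.** With equal shares marked and the same gap in both modalities, the change is 0.000. With 50% marked in one modality and 40% in the other, and every marked non-cancer shifted by 10 points, it is 0.008 to 0.009 in size. The primary non-inferiority margin is 0.05.

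**The case for a change.** The best case for acting is that this is a pilot whose purpose is to supply planning estimates, and it is the natural place to learn how often the two ratings differ. The reader form is headed for both the pilot and the pivotal protocol, so the same two layers seem set to be collected again. Protocol 7.1 singles out biopsy benign and recall cases, where one read crossing the cutoff moves a reader's subgroup specificity by 1/17 = 0.059 or 1/19 = 0.053. Footnote 2 discloses the truth-dependent scoring but does not measure its effect, and no planned output would.

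Part of this stands. The ratings can differ, their discordance rate is unknown, and the explanatory sentences in Protocol 11.3.3 and the Table 5 BI-RADS cell do not match SAP Table 1. The rest does not carry to a change:

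- The AUC shifts only relative to another scoring convention, and neither convention is the true value. If the pivotal study scores as the pilot does, AUC under this rule is the right planning input. The pivotal SAP is not available, so that is an assumption.
- Repeating the analysis with the highest lesion rating in non-cancers would not be like for like. Findings rated 5 and 3, with only the 3 matched, make a cancer a false negative; the same marks make a non-cancer a false positive. The maximum also rises with the number of marks. A difference between the two analyses could not be attributed to the rating source alone.
- Both ratings are on the form, so a count can be produced at any time without being pre-specified.

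**Conclusion.** No change to the plan is needed. The scoring rule can be executed as written, is the same in both documents for the primary endpoint, and follows from the localization requirement. The BI-RADS mismatch is a clerical slip in the protocol that the precedence clause already resolves; correcting it would alter no planned result.

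The effect is at most 0.002 per discordant read in the six-reader average, and about 0.003 to 0.004 in a single reader's AUC in the moderate assumed case. It disappears from the between-modality difference when marking and discordance are alike in the two modalities. Larger shifts, up to about 0.04 in a within-modality AUC in the 40%-marked scenarios tabulated, need every marked non-cancer to be discordant by 10 points in the same direction. These AUC figures rest on assumed POM distributions and marking rates. The exact bounds rest only on the case and reader counts. A tabulation of how often the overall and highest lesion ratings differ would be a reasonable descriptive extra, at the analysts' discretion.

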**Table 2. Per-Subject Recall Scores Requiring Correct Lesion Localization**

Reference standard	Reader's interpretation	Per-Subject Recall Score
No malignancies in this case	No recall	Same as recall recorded by the reader for the case, that is, no recall.
	Recall	Same as recall recorded by the reader for the case, that is, recall.
One or more malignancies in this case 	No recall	Same as recall recorded by the reader for the case, that is, no recall.
	Recall and Findings in this case, but no findings matching the location(s) of any proven malignancies in this case	Assigned as no recall.
	Recall and One or more findings correctly matching the location(s) of any proven malignancies in this case	Same as recall recorded by the reader for the case overall.

If the case contains more than one malignant lesion, the reader will get credit for recalling the case even if the reader does not identify all of the proven malignancies in the case. For example in a bilateral case, the reader would get credit for recalling the case even if the reader marks findings in only one breast as long as the overall decision is to recall the subject.

## **4.6. Analysis of Study Endpoints and Important Subgroups**

### **4.6.1. Primary Endpoint**

The primary endpoint on this study is non-inferior per-subject average AUC requiring correct lesion localization. We will estimate AUCs for each reader in each review condition (FFDM, DBT plus S-View) based on per-subject POM scores requiring correct lesion localization derived as in **Section 4.4**, above. The non-inferiority margin for this endpoint is delta = 0.05.

Primary analysis will not involve pooling across study radiologists, to allow for heterogeneity across them. We will provide graphs of each reader's ROC curve for each review condition. For each reader, the non-parametric (trapezoidal) AUC for the FFDM read, the DBT plus S-View read, and the difference between them, will be presented. Statistical inferences will account for correlations arising from having all study readers interpret all study cases. We plan to compare AUCs between reading conditions using the standard MRMC analysis of variance (ANOVA) method of Obuchowski and Rockette, to ensure generalization of the study results to both the population of readers and the population of cases. Two-sided 95% CIs will be used to quantify uncertainty in the within-modality estimates and the between-modalities differences.

Information on the magnitude and direction of differences between AUCs for the two modalities, and variance components and correlations that influence sample sizes and case mix for the pivotal reader study comparing AUCs between the two modalities, will be obtained from this MRMC analysis.

### **4.6.2. Secondary Endpoints**

The following secondary endpoints will be explored in this pilot study, in order to best plan for the secondary endpoints for the pivotal study. Per-subject recall, BI-RADS, and POM scores requiring correct lesion localization will be derived as described in **Section 4.4**. Analyses of secondary endpoints also will be performed using standard MRMC ANOVA methods, with two-sided 95% CIs used to quantify uncertainty. The secondary endpoints are:

1. Superior per-subject average AUC for DBT plus S-View versus FFDM.
2. Non-inferior and/or superior (lower) per-subject average recall rate for all non-cancer cases for DBT plus S-View versus FFDM, using non-inferiority margin delta = 0.05.

3. Superior per-subject average specificity for DBT plus S-View versus FFDM, based on BI-RADS scores.
4. Non-inferior and/or superior per-subject average sensitivity for DBT plus S-View versus FFDM, using non-inferiority margin delta = 0.10.
5. Non-inferior per-subject average recall rate for DBT plus S-View versus FFDM for all cancer cases, using non-inferiority margin delta = 0.10.

#### **4.6.3. Important Subgroups**

If performed, analyses in important subgroups also would employ standard MRMC ANOVA methods, with two-sided 95% CIs used to quantify uncertainty. The subgroup of soft tissue lesions (masses with or without calcifications, focal asymmetries, and/or architectural distortions) includes a cancer case with two malignant masses in the right breast. To account for this clustering, prior to the MRMC ANOVA we would use Rao and Scott's method for clustered data to estimate sensitivity and Obuchowski's extension of this to estimate the variance-covariance matrix of all possible pairs of sensitivities across readers and review conditions.

